2.13 Missed Visits

If participant misses a follow-up appointment, participant should be immediately rescheduled.

If the participant is unable to be rescheduled, the participant should complete the RAPID survey by telephone or by a password protected REDCap link to the HIPAA compliant RAPID website. Participant will receive \$10 for completion of the RAPID survey.

2.14 Participant Withdrawal (Appendix 2-I, Withdrawal Form)

Participants will be free to withdraw from the study at any time with no penalty.

Participants may be withdrawn from the study if the study clinician determines it is not in the best interest of the participant to continue.

Participant may be withdrawn from the study if clinical features of the conjunctival infection change during follow-up in a manner to indicate a non-adenoviral infection (e.g. bacterial, herpetic). Participants who develop known complications of adenoviral infections including corneal subepithelial infiltrates decreasing visual acuity two lines or more, a conjunctival pseudomembrane or a conjunctival membrane, will continue in the study and will be managed according to standard clinical care with the most appropriate therapy.

2.15 Infection Control Protocol

In compliance with the findings from the 2006 Rutala et al study and the CDC Guideline for Disinfection and Sterilization in Healthcare Facilities”,⁽⁶⁶⁾ hypochlorite bleach wipes (1:10 dilution) will be used to disinfect all counter-tops, chair surfaces, handled equipment, chin and forehead rests, and door knobs. All surfaces will be disinfected immediately following each visit. The 1:10 dilution complies with the CDC guidelines.

1. Participants who present with “pink eye” will be ushered directly to a designated “red eye” examination room. If one is not available, the patient will be ushered to a designated “red eye” chair in the waiting room.
2. Magazines adjacent to chair will be disposed of afterwards in red biohazard bag. The chair surface will be disinfected with hypochlorite bleach or cavicide wipes.
3. Upon entering the “red eye” examination room, the study certified clinician/technician will request the patient to wash their hands. The clinician/technician will turn on the water and dispense soap. The patient dries hands and disposes of paper towels in red biohazard bag.
4. Two copies of the consent form are signed. The clinic files one in a red folder indicating biohazard. The other copy is given to the patient along with the pen used to sign.
5. Label vial of Universal Viral Transport Medium and apply barcode prior to beginning examination. Write patient ID and visit date on RPS test cassette with Sharpie® permanent marker prior to beginning examination.
6. The clinician/technician dons gloves.
7. After the examination is completed, the clinician/technician disposes of their gloves in the red biohazard bag and will request the patient to wash their hands again. The clinician/technician will turn on the water and dispense soap. The patient dries hands and disposes of paper towels in red biohazard bag.
8. The clinician/technician disinfects all surfaces with hypochlorite bleach or cavicide wipes including:
 - Chair
 - Slit lamp microscope
 - Handheld occluder
 - Proparacaine bottle and paint chip

2.16 Reporting of Adverse Events (AE) (Appendix 2-J, Adverse Events Form)

Participants will be instructed to contact the study investigator immediately should an AE occur. All AE’s will be documented on AE forms and entered into a computer-based log. The masked clinician grades AE severity: 1) minimal discomfort 2) moderate discomfort limiting daily activities, or 3) major discomfort requiring medical care and judges “relatedness” of AE to treatment as “Definitely not related” “Possibly related”, “Definitely related”.

Serious adverse events will be reviewed electronically within 24 hours of notification of the Coordinating Center by the Steering Committee and the Data Monitoring and Oversight Committee. Routine review of AE’s will be done weekly by the Steering Committee and quarterly by the Data Monitoring and Oversight Committee.

2.17.1 Participant Reimbursement

Participants completing 5 F/U visits at 1-2 days, 4, 7, 14 and 21 days will be reimbursed \$20 per completed visit for \$100 total. Parking costs, if applicable, will also be reimbursed. Participants who miss a visit but complete RAPID survey questions on the follow-up form by phone or on the HIPAA compliant study website will be reimbursed \$10 as well. Clinical staff will complete reimbursement voucher for each completed visit within 3 working days and transmit the form via REDCap to the Coordinating Center. Reimbursement will be by a gift card in the amount of \$20 or a check mailed directly to the participant for \$10 for completion of the survey and/or \$20 for each completed visit.

2.17.2 Clinic Reimbursement

Clinics may elect to forego or, if necessary, can request to receive up to \$50 per follow-up research visit to cover some of the costs of participant follow-up, data collection and data entry. Clinic reimbursement does not include the screening/baseline visit nor follow-up visits that are considered standard of care. Some clinics will charge off follow-up research visits as “research” and not charge the study.

2.18 Methods to Minimize Bias

The following measures will be undertaken to reduce potential bias:

1. Masked, centralized randomization;
2. With the exception of the one-time, in-office application of artificial tears or 5% PVP-I at baseline, all participants will undergo the same follow-up treatment (artificial tears), measures and procedures during the follow-up visits;
3. Study entry requires a positive AdenoPlus™ test, an unbiased and objective criteria compared to signs/symptoms assessed by clinicians;
4. Separation of treating clinician/technician from the masked clinician/technician who conducts follow-up visits and records post-treatment clinical outcome measures;
5. All eyes are lavaged with saline to reduce residual staining that could unmask participants who receive 5% PVP-I;
6. The primary outcome is change in viral titers as measured by qPCR which is standardized, quantitative, performed by an independent laboratory and not subject to examiner bias.

Missed visits will be minimized by giving participants the clinic contact information (telephone number, cell number of PI, e-m address), List of dates/times of F/U visits and by remuneration of \$20 for each completed follow-up visit and \$10 for completion of the survey by phone or by secure internet.

2.19 Data Entry Software

REDCap data entry system is a secure, web-based data capture and management system that is currently in use in over 1,311 active institutional partners involving over 149,000 projects worldwide. Data entry screens are customized for each project and study variables can be drawn from a large dictionary of standard clinical and demographic variables, names and formats. The Division of Biostatistics is the Informatics Core that manages the system for the entire Washington University system. DES is installed on the private zone of the cluster of Linux servers in the Division of

Biostatistics. The private network is protected from the rest of the University by a Linux firewall, and the University system is protected from the world by another firewall. The DES is password protected and uses a multi-level login system that regulates access corresponding to approval level.

2.20 Timeline

The Steering Committee has met by teleconference weekly since the fall of 2012 and will continue to do so.

- < Month 1 February, 2015: Complete provisional protocol and operational description for R-34 planning study, case report forms, web data entry and randomization system, IRB submission/approvals.
- Month 1-5 February-June 2015: Face-to-face Steering Committee meeting to finalize planning study and train/certify Clinical Center Clinicians, Coordinating Center completes programming for key progress and safety reports for monthly Steering Committee review, purchase & distribute supplies, clinics enroll patients.
- Month 6-12 July-January 2016: Steering Committee will review pre-randomization data (recruitment, exclusions, baseline data, pre-post treatment fluorescein staining, treatment discomfort and masking at 4 days) and post-randomization data including retention, data quality and completeness. Data Monitoring and Oversight Committee will review masked data semi-annually by randomization assignment including qPCR, clinical and pt. reported outcome data and safety data.

Continue enrolling patients and generate quarterly reports on study progress and safety.
- Month 13-18 February-July 2016: Close enrollment, analyses of AdenoPlus™ specificity and differences in viral load and symptoms over time by randomization groups.
- Month 18-24 August 2016-February 2017: Face-to-face Steering Committee meeting to finalize protocol for UG1 clinical trial and MOP chapters.

MEMORANDUM #1

TO: RAPID Study Clinicians
FROM: [name], MS, OD 
SUBJECT: Protocol Clarification
DATE: January 21, 2018

The purpose of this communication is to clarify when patients that do not meet the eligibility criteria are exited.

If patients do not meet age or disease duration criteria, no further questioning or testing is performed. If it is determined on Page 1, Item #1 of the RAPID: Screening/Baseline Form that the patient is not at least 18 years of age, the patient is exited at this point. Ensure that the first affected eye has been symptomatic for no more than four days. This will be queried on Page 2, Item #5 (right eye) or Item #7 (left eye). If the patient reports a red eye in the first involved eye of more than four days, the patient is exited at this point and no further testing is performed.

If a patient is at least 18 years of age and the first affected eye has been symptomatic for no more than four days, complete the ENTIRE screening form asking all questions and performing all testing including RPS and qPCR tear sampling. Patients who do not meet all of the eligibility criteria (e.g. history of thyroid disease, allergy to Betadine, etc.) will not be randomized but it will still be useful for the study to collect all screening information on these patients who are eligible to be screened. The one testing exception is that patients who will not be randomized do NOT need to complete a pregnancy test.

This is not a change in the protocol, merely clarification. Please contact any member of the RAPID steering committee if you have any questions.

2.21 Statistical Analysis Plan: Primary Efficacy Outcome

RAPID is a National Eye Institute funded R-34 planning study. The target sample size of 40 (20 per group) is selected assuming a large effect size of 0.80, power = 0.80, and a nominal two-sided alpha of 0.05. To decrease the probability of failing to reject a null hypothesis, there is no correction for multiple comparisons.

The primary efficacy outcome is reduction from peak viral load defined as the percent reduction of DNA copies per ml from the participant's peak viral load. The Data and Safety Monitoring Committee approved a modified intention to treat analyses (mITT) to test efficacy outcomes in participants with detectable viral load by qPCR at baseline. The mITT analysis should not bias efficacy results because samples for qPCR were taken from all screened patients prior to randomization and qPCR results were never disclosed to participants or study personnel. Safety is assessed using all randomized participants per intention-to-treat.

The primary outcome and other quantitative variables including symptoms and signs will be analyzed using nonparametric Wilcoxon rank order tests. The exact p-value will be calculated by a computational network algorithm (Mehta and Patel, 1983) given that asymptotic results assuming a normal distribution cannot be assumed with small sample sizes. Nominal variables will be analyzed using Fisher's exact test. Treatment "effect size" (PVP-I mean minus AT mean divided by their standard deviation) will be calculated for the primary outcome to supplement p-values. Cohen has classified effect sizes of 0.2 as "small", 0.5 as "medium" and 0.8 as "large". (REF: Cohen J. Statistical Power Analysis for the Behavioural Sciences. 2nd ed. Hillsdale, NJ: Erlbaum Associates; 1988.)

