2.0 Study Design

Summary of Reducing Adenoviral Patient-Infected Days (RAPID) Study

This is a double-masked, randomized pilot study to estimate planning parameters for a definitive large scale trial. In the pilot study, we will randomize 50 participants with adenoviral conjunctivitis confirmed by qPCR in 1:1 ratio to either one-time, in-office treatment with artificial tears or povidone iodine 5% (5% PVP-I). Follow-up care in both groups after treatment at baseline will be standard of care with single-use artificial tears 4 times-a-day until resolution of symptoms. The pilot study is funded by a NIH R-34 Planning Grant.

Key Eligibility Criteria

1. Ability to provide written informed consent;
2. At least 18 years of age, male or female, of any race;
3. Self-reported onset of symptoms in first affected eye \leq 4 days of presentation;
4. Adeno-viral conjunctivitis in study eye confirmed by RPS AdenoPlus™;
5. Females capable of becoming pregnant must have negative urine pregnancy testing.

Key Exclusion Criteria

1. History of hypersensitivity to iodine or Betadine™ or thyroid disease;
2. History of herpetic eye disease;
3. Ocular surgery in study eye within the past 3 months;
4. Presence of skin vesicles, corneal subepithelial infiltrates, corneal dendrites, traumatic corneal abrasion, corneal ulcer, foreign body, or conjunctival membrane/pseudomembranes, or anterior chamber cell or inflammation in study eye on slit lamp examination;
5. Females who are pregnant or lactating or have positive urine pregnancy test.

Study Visits

Screening/Baseline visit includes completion of RAPID symptom survey, a comprehensive eye examination including visual acuity, SLE, fluorescein staining, RPS AdenoPlus™ and tear sampling for molecular diagnosis.

Eligible patients are randomized to receive one-time, in-office dose of 5% PVP-I or artificial tears at baseline and complete 5 f/up visits (1-2, 4, 7, 14 and 21 days). Tear samples for molecular diagnosis are taken at each f/up visit and AdenoPlus™ testing continues til 2 consecutive negative tests.

Ineligible patients will receive standard of care outside of the RAPID study.

Unmasked clinician/technician administers randomized treatment.

Masked clinician/technician completes all follow-up visits.

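### The primary outcome's effect size is a mean-over-SD ratio on a capped percent scale, with the SD undefined and no confidence interval, beside a rank test in a planning pilot

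*Combined protocol and SAP*

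**What the plan says.** Section 2.21 defines the primary outcome as the "percent reduction of DNA copies per ml from the participant's peak viral load". It is tested with a Wilcoxon rank test and an exact p-value, because asymptotic normal results are not trusted in small samples. As an addition to the p-value, the section plans a treatment effect size, "PVP-I mean minus AT mean divided by their standard deviation", to be read against Cohen's benchmarks of 0.2, 0.5 and 0.8.

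The section does not state which SD is meant (pooled, control arm or all participants) or the time point at which the reduction is measured. No CI is planned for any quantity in the protocol or the SAP.

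Section 2.0 describes the study as a "randomized pilot study to estimate planning parameters for a definitive large scale trial". The one explicit rule for sizing UG1 is in section 2.1, Aim 1: an adjustment for false-positive AdenoPlus results.

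**The concern.** There are two separate problems.

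- **Precision.** A planning study should show how uncertain its effect estimate is. With about 20 per group a standardised difference is very imprecise, and a single value set beside Cohen's labels hides this. Anyone who took it as an input for UG1 could be wrong by a large factor in either direction.
- **Scale.** Percent reduction from a participant's own peak cannot exceed 100%, and cannot fall below 0% if the peak is the participant's maximum. As both arms clear virus, values pile up near 100%. Means and SDs on that scale then reflect the distance from the cap as well as the difference between arms. The Wilcoxon test uses ranks and is largely unaffected, so the effect size and the test it accompanies can tell different stories.

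**Working it through.** **Inputs from the documents.** Section 2.21: "The target sample size of 40 (20 per group) is selected assuming a large effect size of 0.80". It also sets 80% power and a two-sided 5% significance level. Section 2.0 gives 50 participants, 1:1, so 25 per arm.

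**Assumptions, not in the documents.** The observed effect size d equals the design value of 0.80. For the scale check, log10 reduction L is normal with SD 1 or 1.5, the control mean is 0.5 to 3 log10, the treated mean is 0.8 SD higher, and L is floored at 0.

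**Step 1: the plan's own figure.** n per group = 2(1.960 + 0.842)²/d² = 15.70/d². At d = 0.80 this is 15.70/0.64 = 24.5, so 25. A t-test needs about one more (25.5, so 26). The stated 20 does not reproduce under a two-sided 0.05. It matches a one-sided 0.05: 2(1.645 + 0.842)²/0.64 = 12.37/0.64 = 19.3, so 20. That is a separate matter; here 20 serves only as the stated group size.

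**Step 2: the missing interval.** With 20 per group, t = 0.80 × √(20/2) = 2.53 on 38 degrees of freedom. The noncentrality values that put 2.53 at the upper and lower 2.5% points are 0.474 and 4.555. Dividing by √10 = 3.162 gives 0.150 and 1.440. The t-test size at each limit is close to 15.70/d² + 1:

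| n per group | Level | Interval for d | n per group at lower limit | at 0.80 | at upper limit |
|---|---|---|---|---|---|
| 20 | 95% | 0.15 to 1.44 | 699 | 25.5 | 8.6 |
| 20 | 80% | 0.37 to 1.22 | 113.8 | 25.5 | 11.6 |
| 25 | 95% | 0.22 to 1.37 | 327.5 | 25.5 | 9.4 |

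The lower limits at 20 per group imply a trial about 27 times (699/25.5) or 4.5 times (113.8/25.5) the size implied by the point value.

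**Step 3: the cap.** Percent reduction = 100(1 − 10^−L). Simulated with 2 million per arm, true log10-scale d = 0.80, pooled SD; n = 15.70/d² from unrounded d:

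| Control mean (log10) | Mean % by arm (SD 1) | Percent-scale d, SD 1 | SD 1.5 | Implied n per group, SD 1 | SD 1.5 |
|---|---|---|---|---|---|
| 0.5 | 53.2 v 79.1 | 0.70 | 0.69 | 32 | 34 |
| 1 | 70.5 v 89.5 | 0.63 | 0.64 | 41 | 39 |
| 2 | 92.3 v 98.2 | 0.41 | 0.49 | 94 | 67 |
| 3 | 98.8 v 99.8 | 0.23 | 0.32 | 291 | 155 |

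The log10-scale d gives 25 to 27 throughout. The probability of superiority is Φ(0.80/√2) = 0.714 before flooring and 0.709 to 0.714 in these rows. By Noether's formula a Wilcoxon test needs about (1.960 + 0.842)²/[6(0.714 − 0.5)²] = 28.6, so 29 per group (30 in the 0.5 log10 rows).

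**Step 4: what a pilot of 20 per arm would show.** These percent-scale values are population values. In simulated pilots with log10 SD 1, the median sample d is 0.64, 0.50 and 0.45 at control means of 1, 2 and 3 log10, with central 95% ranges of 0.02 to 1.23, −0.16 to 0.86 and −0.21 to 0.86. At 3 log10 a typical pilot would thus imply 15.70/0.45² = 77.5, so 78 per group and not 291. The noncentral-t interval is only approximate on this scale.

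**The case against.** The strongest reply is that this is a supplementary statistic. The primary test and p-value are unaffected, and a reader can compute an interval from d and the group sizes. The first half stands and limits the weight of the point. The second half stands only in part, because the SD is undefined and the usual interval assumes normal data.

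Several stronger readings are tempting, but the documents do not support them.

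- **That this effect size is designated to size UG1.** A reader might infer it from the pilot's purpose. Section 2.21 gives the statistic only as an addition to p-values, and Aim 1 contains the only UG1 sizing rule.
- **That it is the study's only output on viral load.** Aim 2 will quantify viral-load change at each visit, and section 2.20 plans comparisons between groups over time. Neither is given an interval.
- **That the SAP concedes percent reduction is non-normal.** Its remark concerns asymptotic results in small samples, not this scale.
- **That d on this scale reflects closeness to 100% and not the arm difference.** It depends on both.
- **That the cap must distort planning several-fold.** The documents give no clearance or SD. At control reductions of 0.5 to 1 log10 the inflation is about 1.2- to 1.6-fold. In this model the cap shrinks the population d, which would oversize UG1, not leave it underpowered. If UG1 kept a percent endpoint with a mean-based test, percent-scale d would be the matching input.

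Two further objections stand. Changing the scale does not cure imprecision, since a log10 effect size has an equally wide interval. And log10 reduction is undefined for an undetectable sample, with no detection limit in the documents.

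**Conclusion.** The point holds as a low-cost reporting improvement. Section 2.21 summarises the treatment effect on the primary outcome only as a mean difference over an unspecified SD, on a capped scale, without an interval.

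The precision part needs no outside data beyond an assumed observed d of 0.80: the plausible effect runs from trivial to very large. That matters for UG1 only if the point value is used there, which the documents leave open.

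The scale part is certain in kind and uncertain in size. It is modest at low clearance and about 2.7-fold (67/25) to 12-fold (291/25) in population terms at 2 to 3 log10. It rests wholly on the assumed values, and the unstated time point leaves open where in that range the trial would fall.

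**What to change.** In section 2.21:

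1. Report the probability of superiority, corrected for ties, with a 95% CI. It matches the Wilcoxon test and needs no log transformation.
2. If the effect size is kept, state that the SD is pooled, and give a 95% CI with its method named.
3. Add, as a companion, the Hodges-Lehmann difference or d in log10 reduction with a 95% CI. Set undetectable samples to a prespecified value at the assay's detection limit. Many ties would make the Hodges-Lehmann interval approximate.
4. State that any use of these results for UG1 planning draws on the interval, not on the point value.

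The cost is SAP wording, one table and a detection-limit rule to be agreed with the laboratory. The primary outcome, the test and the data collection do not change. The drawback is that a wide interval makes the pilot look less conclusive.
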